The optimal frequency, duration and number of tDCS sessions to maximize effects on craving, or any other construct in this young field, remain obscure. We chose to deliver 5 sessions of tDCS because this number has been used in prior successful tDCS craving interventions and must be balanced against adherence concerns. While we are hopeful that participants will complete 5 consecutive days of tDCS, the interruption of weekends and the transition from the ADP setting (where the tDCS protocol will start) where days are structured, to the community setting, raises the possibility of missed tDCS sessions and therefore we will allow these 5 sessions to occur over 10 days if necessary, as has been described in prior studies, tracking both average number of sessions received and period of treatment for analyses. The sham tDCS condition is included in our design to separate the effects of ongoing opioid treatment from the effect of active tDCS on craving. We decided not to include a third no-tDCS arm, as this would omit any nonspecific treatment effects (match for attention, expectation) of entering a neurostimulation treatment protocol. This protocol will provide a basis for future studies of tDCS stimulation parameters (frequency, duration, number) that could optimize adherence and treatment effects of drug use outcomes.

In phase two (UH3), we will perform a larger RCT using the same treatment protocol in 100 opioid dependent participants who recently initiated buprenorphine or methadone. Participants will be randomized to receive five sessions of tDCS+CCN priming stimulation vs. sham tDCS+CCN priming. Phase two will address long-term (3-month) neurobehavioral outcomes, including opioid relapse, craving, and sustained fMRI changes during a paradigm that challenges networks associated with craving (CR) and cognitive control (CCN). During the 12 weeks of opioid maintenance treatment, we will examine our primary clinical outcome, relapse (opioid use on >4 days per month and having an opioid positive urine screen), as well as days of opioid use.

2.c Inclusion/Exclusion Criteria:

UG3/UH3 Inclusion Criteria: (a) current opioid dependence, (b) between 21-50 years of age, (c) recent initiation of buprenorphine or methadone (<30 days)

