Exclusion Criteria: (a) diagnosis of organic brain disorder, bipolar disorder, schizophrenia, schizo-affective, schizophreniform, or paranoid disorder, (b) current suicidality, (c) evidence of neurocognitive dysfunction, (d) contraindications for tDCS (e.g seizure disorder), (e) probation/parole requirements or an upcoming move that might interfere with protocol participation, (f) planning to terminate buprenorphine or methadone in less than 3 months, and (g) scalp lesions near the tDCS electrode sites.

Exclusion Criteria related to FMRI scanning are: (a) history of neurological disorder (e.g., epilepsy, stroke, brain injury with loss of consciousness>10 min), (b) impaired uncorrected vision, and (c) MRI contraindications (e.g., claustrophobia, specific metallic implants and injuries, and pregnancy).

tDCS-related considerations: Careful consideration will be given when determining whether tDCS is safe for potential participants. Additional exclusion criteria related to tDCS include: metal implanted in the cranial cavity, pacemaker, poor cognitive functioning (i.e., Alzheimer's disease or dementia), history of neurological disorder (e.g., epilepsy or other seizure disorder), or other significant or chronic medical conditions that affect the brain (e.g., Parkinson's disease, Huntington's disease, multiple sclerosis, traumatic brain injury). [name] will have the final decision regarding whether a participant is medically stable enough to engage in this trial.

2.d Power Calculation and Sample Size:

In the UG3 phase of this project, we plan to enroll 60 participants. With an expected attrition rate of 20% (data loss over two sessions due to poor performance or movement artifact—a conservative estimate that is a larger loss than in our ongoing FIRST study), our final sample size will be 48, or 24 per group. This number provides 82% power for the expected effect size of .75, chosen based on prior tDCS studies and our belief that a large effect size should be required to continue to the UH3. In the UH3 phase, we again anticipate a 20% attrition rate over the 5 tDCS sessions and initial two fMRI scans. If the third scan (at 4 weeks) is missed, we expect this will be due to treatment drop-out or relapse. With 100 participants enrolled, we will have a final sample of 80 patients which provides a power of .8 to detect a group difference in relapse between relapse and sham of 15% vs 39% at 3 months follow-up.

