1) CR: Two 2x2 mixed ANOVAs will be used to determine whether mean response to cues during CR decline across nodes of the craving network (VS, amygdala, VMPFC), including salience network (AI, ACC) and increases in the CCN (MFG, IPL). Significant pre-post main effects and group x treatment interactions are predicted in each. Those who received tDCS+CCN priming are expected to exhibit greater change. Follow up analyses of individual nodes within each network and whole-brain voxel-wise contrasts will be conducted to inform phase 2 analyses.

2) n-Back: Two 2x2 mixed ANOVAs will be used to determine whether mean response to the n-Back challenge increases across nodes of the CCN (MFG, IPL) and the salience network (ACC and AI). Significant pre-post main effects and group x treatment interactions are predicted in each. Those who received tDCS are expected to exhibit greater change. Follow up analyses of individual nodes within each network and whole-brain voxel-wise contrasts will be conducted to inform phase 2 analyses.

3) Resting state: Two 2x2 mixed ANOVAs will be used to determine whether mean network coherence (functional connectivity) decreases across nodes of the craving network (VS, amygdala, VMPFC), including the salience network (AI, ACC) and increases in the CCN (MFG, IPL). Significant pre-post main effects and group x treatment interactions are predicted

in each. Those who received tDCS are expected to exhibit greater change. Parallel exploratory analyses will be conducted to examine resting state functional connectivity of the salience network and DMN.

In the UH3, neuroimaging analyses will generally parallel those described for UG3. We will use a 2x3 ANOVA (three time points) to test the hypothesis that tDCS+CCN priming will be superior to sham tDCS+CCN priming on both subjective and fMRI measures of craving and cognitive control at the end of 5 sessions and at 3-months post tDCS. This same analytical method will be used to test the effect of intervention on days of drug use at the end of 5 sessions and at 3-months. We will use the Pearson χ^2 -test of independence to compare tDCS+CCN priming to sham tDCS+CCN priming on relapse at 3-months.

FMRI data analyses

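### The UH3 primary relapse test has no stated analysis set and no rule for a missing urine or relapse result, and the attrition behind its power figure is ambiguous

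*Combined protocol and SAP*

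**What the plan says.** - **Outcome.** Section 2.a, 2.b makes the UH3 primary clinical outcome "relapse (opioid use on >4 days per month and having an opioid positive urine screen". Both components are required.
- **Test.** Section 4.c uses a Pearson chi-square test "to compare tDCS+CCN priming to sham tDCS+CCN priming on relapse at 3-months". That sentence is the whole stated analysis of relapse. Nothing in the document says who is in the denominator or how a missing urine or relapse status is scored. The only attrition rule in 4.c selects covariates for the EEG analyses at end of stimulation.
- **Sizing.** Section 2.d: "we again anticipate a 20% attrition rate over the 5 tDCS sessions and initial two fMRI scans". From 100 enrolled, "we will have a final sample of 80 patients which provides a power of .8 to detect a group difference in relapse", the difference being "15% vs 39% at 3 months follow-up".
- **Later absence.** Section 2.d also says: "If the third scan (at 4 weeks) is missed, we expect this will be due to treatment drop-out or relapse". It gives no rate and no scoring rule.
- **Meaning of attrition.** For the UG3, 2.d explains its 20% as "data loss over two sessions due to poor performance or movement artifact". For the UH3 it gives no such explanation.
- **Missed sessions.** Section 2.a, 2.b allows the five sessions to spread over 10 days, "tracking both average number of sessions received and period of treatment for analyses".
- **Follow-up.** Section 6.a, 6.c lists UH3 assessments at weeks 2, 4, 6, 8 and 12. Section 2.a, 2.b examines relapse and days of use during the 12 weeks, and 4.c analyses days of use at the end of the sessions and at 3 months. No urine schedule is given.

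**The concern.** The definition joins its two parts with *and*. Read literally, a participant who stops attending and gives no urine cannot be a relapse, so that person is either dropped or counted as not relapsed. The plan's own expectation for a missed third scan is drop-out or relapse. Absence is therefore expected to carry information about the outcome, and the default scoring runs against that expectation.

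Three choices remain open: drop, score as non-relapsed, or score as relapsed. With no rule written down, the choice can be made after the data are seen. Equal loss in the two arms mainly costs power. Unequal loss can bias the comparison in either direction, and scoring every missing result the same way does not remove that bias.

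The sizing adds a second uncertainty. The whole 20% is used up by the second scan, but the outcome is read at 3 months.

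**Working it through.** **Inputs.** From 2.d: relapse 15% vs 39%, 100 enrolled, 20% attrition, stated power .8. Assumed, because not stated for this test: 1:1 allocation and alpha 5%. Sidedness is also unstated, so both versions are shown.

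**1. The planned sample.** 100 × (1 − 0.20) = 80, or 40 per arm. Nothing of the 20% is left for loss after the second scan.

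**2. The plan's power.** Pooled-variance normal approximation:

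power = Φ{ [|p2 − p1| − z√(2p̄(1 − p̄)/n)] / √[(p1(1 − p1) + p2(1 − p2))/n] }

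With p̄ = 0.27 and n = 40, the null standard error is √(0.3942/40) = 0.0993 and the alternative one is √(0.3654/40) = 0.0956.
- Two-sided: (0.24 − 1.96 × 0.0993)/0.0956 = 0.475, power 68%.
- One-sided: (0.24 − 1.645 × 0.0993)/0.0956 = 0.803, power 79%.

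The stated .8 is met approximately only one-sided.

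**3. Power under other denominators and rules** (same formula):

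| Case | Per arm | Two-sided | One-sided |
|---|---|---|---|
| All 100 followed, same rates | 50 | 78% | 86% |
| The 80, no later loss | 40 | 68% | 79% |
| Assumed further 10% loss, complete cases | 36 | 64% | 75% |
| Assumed further 20% loss, complete cases | 32 | 58% | 70% |
| All 100, 20% per arm missing, scored non-relapsed (12.0% vs 31.2%) | 50 | 65% | 76% |
| All 100, 20% per arm missing, scored relapsed (32.0% vs 51.2%) | 50 | 50% | 62% |

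For the last two rows, the scored rate is 0.8p (non-relapsed) or 0.2 + 0.8p (relapsed).

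**4. Can the rule decide the result?** Pearson chi-square without continuity correction, 10 missing per arm. For example, 6/40 vs 15/40 gives 80 × (6 × 25 − 34 × 15)²/(40 × 40 × 21 × 59) = 5.23, p=0.022.

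| Completers | Dropped | Non-relapsed | Relapsed |
|---|---|---|---|
| 6/40 vs 15/40 | 0.022 | 0.027 (6/50 vs 15/50) | 0.067 (16/50 vs 25/50) |
| 6/40 vs 16/40 | 0.012 | 0.016 (6/50 vs 16/50) | 0.043 (16/50 vs 26/50) |

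The first row crosses 0.05 and the second does not. The planned 39% of 40 is 15.6, so the second row is the nearer of the two.

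**5. False-positive rate under unequal loss.** Exact binomial enumeration of the two-sided 5% Pearson test, 50 randomised per arm, true relapse 39% in both arms, loss unrelated to relapse within arm. The loss splits are assumptions.

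| Loss, active vs sham | Scored non-relapsed | Scored relapsed | Complete cases |
|---|---|---|---|
| 30% vs 10% | 13% (27.3% vs 35.1%) | 25% (57.3% vs 45.1%) | 5% (35 vs 45 analysed) |
| 25% vs 15% | 7% | 10% | not tabulated |
| 20% vs 20% | 5% | 6% | not tabulated |

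At 30% vs 10%, nearly all the errors favour active when missing is scored non-relapsed, and sham when it is scored relapsed. Swapping the loss rates between arms swaps the direction.

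**The case against.** **Later loss may already be covered.** The word *again* in 2.d ties the UH3 attrition to the UG3, where it meant unusable data. On that reading up to 100 people may have a relapse status, and a test sized on 80 leaves room for 20 later losses. This stands: the unbudgeted-loss point is conditional on attrition meaning departure from the study. It does not supply an analysis set or a missing-data rule.

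**Interim data exist.** Days of use are to be examined through the 12 weeks, with assessments at five time points. Someone lost at week 10 could already have met a per-month definition. This also stands, and a reader should not infer that nothing is collected before 3 months. The urine schedule is not given, however, so the second component may still be missing.

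**Later drop-outs may be meant to count as relapsed.** A reader might infer this from the sentence on the missed third scan. That sentence gives an expected reason for a missed scan; it does not say how relapse is scored at 3 months.

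**The plan may be a completers-only analysis.** A reader might infer this from the 80. But 80 is a planning number, and tracking the sessions received suggests that people with missed sessions stay in analyses. The text settles neither reading.

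**The illustrations can be chosen to look bad.** This is fair. One case changes the p-value rule's conclusion and the other does not. The 30% vs 10% split is hypothetical, the blinded administrator and the sham procedure make a large imbalance less likely, and dropping missing cases keeps the error near 5% under the same assumption. That protection holds only while loss is unrelated to relapse within arm, which is not what 2.d expects of missed scans.

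**Retention measures are in place.** People with an upcoming move that might interfere, or with plans to stop medication within 3 months, are excluded, and staff try to locate those who miss appointments. These should limit loss, but they do not say how it is analysed.

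**Conclusion.** The concern holds, and it should be fixed. The primary relapse comparison has no stated analysis set and no rule for a missing urine or relapse status. The literal definition excludes people without a urine from being counted as relapsed, although the plan links later absence to drop-out or relapse.

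The size depends on assumptions. With 1:1 allocation and 5% alpha, an assumed further loss of 10% costs about 4 to 5 points of power, and 20% about 8 to 10 points. The missing-data rule can move a result across 0.05 but need not. Error inflation requires loss that differs by arm; it is material at 30% vs 10%, smaller at 25% vs 15%, and about absent when loss is equal.

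Two stronger readings go too far. The gap between 68% and the stated .8 should not be put down to missing data: it comes from sidedness and is present before any later loss. Nor do the documents show that the result will be biased; they show that the handling which would determine this is not fixed in advance.

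**What to change.** 1. In 4.c, state that the relapse comparison includes all randomised participants in their assigned arm, whatever the number of sessions completed or the usability of scans. Seek week-12 use days and urine from those who miss sessions or scans.
2. Pre-specify one rule for a missing urine or relapse status that is not non-relapse by default. It should draw on the use data planned across the week 2, 4, 6, 8 and 12 assessments, and the urine schedule should be written down so that the rule can be applied. Add at least one sensitivity analysis under a different assumption, such as missing-as-relapsed or a tipping-point analysis by arm. Missing-as-relapsed should not stand alone, given its behaviour under unequal loss.
3. Say what attrition means in the UH3, and restate the 3-month power with alpha, sidedness and any loss after the second scan.

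The cost is SAP wording, some follow-up effort, a few sensitivity analyses and a less favourable stated power. The 78% two-sided figure is reached only if all 100 are actually followed.

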week 2, 4, 6, 8, 12 assessments, 5 tDCS appointments, 3 FMRI). For monitoring expected adverse effects of tDCS, we use the SAFTEE at each session that includes changes in physical health status. Deaths are reported by significant others when we try to locate participants who missed appointments. Butler Hospital has a psychiatric emergency room available 24 hours a day. All research procedures will be supervised by Drs. [name] and [name] who will be on call 24-hours a day.

Second, all study staff will be trained in the OHRP definitions of adverse events that are also unanticipated problems; serious adverse events; or unanticipated problems that are not adverse events. All study staff are required to report any event that might meet one of these criteria to one of the PIs immediately both verbally and in writing. When necessary, a report of a serious adverse event will result in one of the PIs contacting the participant to further assess the event.

Drs. [name] and [name] will meet weekly with research assistants to review staff experiences with participants. Based on the sources of information detailed above as well as direct patient contact and/or consultation with the scientific team, Drs. [name] and [name] will determine if the event is: a) a serious adverse event that is also an unanticipated problem; b) an unanticipated problem that is not an adverse event. The Butler Hospital IRB require that fatalities related to the study be reported within 24 hours, all other serious adverse events related to the study be reported within 5 business/7 calendar days, and other serious adverse events related to the study be reported at the continuing review (at least annually).

6.d Reporting of IRB Actions to NIDA

All SAEs will be reported to NIDA within 72 hours of the MPIs becoming aware.

6.e Report of changes of amendments to the protocol

Changes to the proposal must be approved by NIDA prior to implementation

6.f Trial stopping rules

This study will be stopped prior to its completion if: (1) the intervention is associated with adverse effects that call into question the safety of the intervention; (2) any new information becomes available during the trial that necessitates stopping the trial; or

6.g Disclosure of Conflict of Interest

[name]: None

[name]: None

[name]: None

[name]: None

7. Trial Safety

7.a Potential Risks and Benefits for Participants

Potential Coercion.

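### Section 2.d dates the third UH3 scan at 4 weeks, section 4.c needs fMRI at 3 months, and the scan count leaves only one scan for the two

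*Combined protocol and SAP*

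**What the plan says.** Four places in the protocol bear on when the third UH3 scan takes place.

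- **Section 2.d (power and sample size).** On losses in UH3, "we again anticipate a 20% attrition rate over the 5 tDCS sessions and initial two fMRI scans". The next sentence dates the following scan: "If the third scan (at 4 weeks) is missed, we expect this will be due to treatment drop-out or relapse". No anchor is given for the 4 weeks.
- **Section 4.c (data analysis plan), UH3 paragraph.** "We will use a 2x3 ANOVA (three time points) to test the hypothesis" that active stimulation is superior to sham "on both subjective and fMRI measures of craving and cognitive control at the end of 5 sessions and at 3-months post tDCS". The paragraph opens by saying "In the UH3, neuroimaging analyses will generally parallel those described for UG3".
- **Section 2.a, 2.b (summary).** "Phase two will address long-term (3-month) neurobehavioral outcomes, including opioid relapse, craving, and sustained fMRI changes".
- **Section 6.a, 6.c (safety contacts).** After baseline, the UH3 contacts are "week 2, 4, 6, 8, 12 assessments, 5 tDCS appointments, 3 FMRI". The scans are given as a count and are not assigned to any week.

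**The concern.** The objective and the analysis plan both promise an fMRI result at 3 months. The only sentence that dates the third scan puts it at 4 weeks. If site staff schedule from 2.d, the 3-month part of the fMRI hypothesis has no observation, and a scan not done at the intended time cannot be recovered later. Any craving rating taken inside the scanner would be missing at 3 months for the same reason.

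The analysis model is affected too. Section 4.c applies the same method to days of drug use, with 3 months as the later time. With a 4-week scan, the third level of the ANOVA would mean one time for fMRI and another for drug use, and nothing in the plan says so.

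**Working it through.** The plan states no figure to reproduce here. The check is a scan count, followed by a test of whether any choice of anchor makes the two times agree.

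**Inputs**
- UH3 scans in total: 3 (6.a, 6.c).
- Scans grouped with the stimulation sessions: the initial two (2.d). This fits the UG3 pattern in 2.a, 2.b of one scan before and one after stimulation.
- Time of the third scan: 4 weeks, anchor not stated (2.d).
- Times at which fMRI is tested: end of stimulation and 3 months after it, within three time points (4.c).
- Stimulation window: "we will allow these 5 sessions to occur over 10 days if necessary" (2.a, 2.b).

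**Step 1: scans available.** 3 - 2 = 1 scan remains after the stimulation period.

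**Step 2: scans needed.** Section 4.c names two of its three time points; I take the other to be the pre-stimulation scan, as in UG3. Before stimulation, after stimulation and 3 months use all 3 scans. So do before stimulation, after stimulation and 4 weeks. Having both later times would need 4 scans and four time points, against the stated 3 and 3. No section describes a fourth scan or takes fMRI out of the 3-month hypothesis.

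**Step 3: can the anchor reconcile the two times?** Let the first session be day 1 and the last session day L (5 to 10), and let the baseline visit fall b days before day 1. The documents do not give b; I assume 0 to 7. I take 3 months as M = 84 to 91 days.

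- Both times counted from the end of stimulation: M - 28 = 56 to 63 days apart.
- 4 weeks from the first session (day 29), 3 months from the end of stimulation (day L + M): from 5 + 84 - 29 = 60 to 10 + 91 - 29 = 72 days.
- 4 weeks from baseline (day 29 - b), 3 months from the end of stimulation: 60 + b to 72 + b, so 60 to 79 days.
- Week 4 and week 12 visits on one grid: 84 - 28 = 56 days.
- 4 weeks from the end of stimulation (day L + 28), with the week 12 visit counted from baseline (day 85 - b) taken as the 3-month time: 57 - b - L. This gives 47 to 52 days for b = 0 and 40 to 45 days for b = 7.

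Under these assumptions the two times are 40 to 79 days apart. In the case with the smallest gap, closing it would need b = 57 - L, a baseline visit 47 to 52 days before the first session.

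**Step 4: which date is meant?** The 6.a list contains both a week 4 and a week 12 assessment and assigns a scan to neither, so it supports both readings equally.

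**The case against.** The strongest reply is that the 4 weeks is a slip. As a scan date it occurs once, in a parenthesis in a sentence about attrition, while the objective and the analysis plan both say 3 months. On that reading the repair is one parenthesis. This is plausible but not proven: 2.d is the only text that dates the third scan, and a week 4 visit exists at which a scan could be done.

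A second reply is that the figure at the start of section 3, which is not shown in the text reviewed, may contain the schedule. It could indicate the intended date. It could not make 2.d and 4.c agree.

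A third reply is that 2.d never calls the third scan the last one. That is correct. That it is the last follows from the count in 6.a and the three time points in 4.c, and the point depends on that inference.

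Stronger readings are tempting, and the documents do not support them:

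- A reader might infer that the 3-month craving result is lost as well. For UG3, section 2.a, 2.b allows craving to be rated in the cue task or outside the scanner. Section 4.c says only that the measure is subjective, and 6.a lists a week 12 assessment apart from the scans. Only a rating taken in the scanner would be lost.
- A reader might infer that the 3-month relapse comparison or its power is undermined. Neither uses a scan.
- A reader might infer that the two dates must be at least 8 weeks apart. The last anchor case in the working gives less, so no such minimum should be quoted.

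**Conclusion.** The contradiction stands and should be fixed. Section 2.d and section 4.c cannot both be right about the third UH3 scan. It affects one of the 3 scans, one of the two post-treatment fMRI time points, and the stated 3-month fMRI objective. The fMRI comparison at the end of stimulation, the relapse outcome, its chi-square test and the stated power are not touched.

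The conclusion rests on two readings: that the count of 3 scans in 6.a is complete, and that the initial two scans in 2.d are those before and after stimulation. It does not depend on the assumed values of b and M, which affect only the size of the gap.

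A reader might go further and conclude that the trial plans no 3-month scan. The documents do not show that; they leave open which of the two times is intended.

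**What to change.** Choose one time for the third UH3 scan, state what it is counted from, and make sections 2.a/2.b, 2.d, 4.c and 6.a agree. Have the fMRI hypothesis and the third level of the ANOVA name that time.

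- If 3 months is meant, correct the parenthesis in 2.d.
- If 4 weeks is meant, limit the fMRI durability claim, and any claim from craving rated in the scanner, to 4 weeks. Say in 4.c that the third level falls at 4 weeks for fMRI and at 3 months for days of drug use.

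The cost is protocol wording, with the NIDA approval that section 6.e requires before a change is implemented. Sample size and stated power stay as they are. If 4 weeks is meant, the further cost is a shorter-term fMRI claim.

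### The plan ties missed third scans to relapse or treatment drop-out, but its UH3 2x3 ANOVA has no missing-data method and, as normally run, would under-represent relapsers, more so in the sham arm

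*Combined protocol and SAP*

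**What the plan says.** Section 2.a, 2.b sets the UH3 aim: "Phase two will address long-term (3-month) neurobehavioral outcomes, including opioid relapse, craving, and sustained fMRI changes". It defines relapse, the primary clinical outcome, by a threshold on days of opioid use per month together with a positive urine screen.

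Section 2.d allows for early loss only: "we again anticipate a 20% attrition rate over the 5 tDCS sessions and initial two fMRI scans". This takes 100 enrolled to 80 analysed. For the third scan it gives an expected cause of loss but no rate: "If the third scan (at 4 weeks) is missed, we expect this will be due to treatment drop-out or relapse". The power statement assumes relapse of 15% vs 39% at 3 months.

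Section 4.c gives the UH3 analysis: "We will use a 2x3 ANOVA (three time points) to test the hypothesis that tDCS+CCN priming will be superior to sham tDCS+CCN priming". The outcomes it covers are the imaging and self-report measures of craving and of cognitive control, with two target times: when stimulation finishes, and 3 months later. Drug use is handled likewise: "This same analytical method will be used to test the effect of intervention on days of drug use". Relapse itself is compared with a Pearson chi-square test.

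For these UH3 outcomes the document names no analysis set, imputation, mixed model or sensitivity analysis. The one attrition-related provision, covariates that predict attrition at end of stimulation, belongs to the EEG analyses.

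**The concern.** The sponsor expects the third scan to be missing for reasons bound up with how the participant is doing. One of those reasons is the primary outcome, which is assumed to be far commoner in one arm. A repeated-measures ANOVA in its usual form needs every time point, and this has two consequences.

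- **Third time point.** The arms would be compared among people selected after randomisation. If active tDCS prevents relapse as assumed, sham loses more of its poor responders than active does. The remaining sham group looks better than it should, and the arm difference shrinks.
- **End of the 5 sessions.** A participant who misses only the third scan also loses valid first and second scans. The early contrast is then conditioned on a later event, although the data for it were collected.

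At stake is the phase-two aim on sustained fMRI and craving change. Section 2.d itself says that the constructs measured by the fMRI paradigms relate to relapse in behavioural studies. The plan therefore gives some reason to expect a link between what is measured and why it goes missing.

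**Working it through.** **Plan's own figure.** 100 x (1 - 0.20) = 80, taken as 40 per arm (1:1 is an assumption for UH3). I read 15% as active and 39% as sham. Power at 40 per arm is 0.789 with a one-sided 0.05 test and 0.683 with a two-sided one, so the stated .8 is reached only one-sided. The document states neither alpha nor sidedness. That is a separate matter and does not affect this point.

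**Assumptions not in the document.** f is the share of 3-month relapsers who miss the third scan. Relapse is the only cause of loss. The third-scan measure has correlation rho = 0.3-0.5 with a normally distributed relapse propensity.

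**Formulas.** With p the relapse rate in an arm:
- kept per arm = 40 x (1 - f p)
- standard error ratio = sqrt[(1/n_active + 1/n_sham) / (2/40)]
- shift of the kept mean, in units of rho SD: phi(z_fp)/(1 - f p) if the relapsers with the highest propensity are the ones who miss, or f phi(z_p)/(1 - f p) if a random share of relapsers miss. Here z_q is the normal quantile with upper tail q.
- bias towards no difference = rho x (sham shift - active shift)

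**Why f = 1/3.** Relapse after week 4 cannot cause a missed scan at week 4. If relapses are spread evenly over 12 weeks, 4/12 of them fall before such a scan.

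| f | Kept active / sham | Total of 80 | SE ratio | Shift difference, highest-propensity loss | Shift difference, random loss | Bias, rho 0.3-0.5 |
|---|---|---|---|---|---|---|
| 1/3 | 38.0 / 34.8 | 72.8 | 1.05 | 0.243 - 0.109 = 0.135 (rounded) | 0.147 - 0.082 = 0.065 | 0.02-0.07 SD |
| 1/2 | 37.0 / 32.2 | 69.2 | 1.08 | 0.342 - 0.153 = 0.189 | 0.238 - 0.126 = 0.112 | 0.03-0.09 SD |
| 1 | 34.0 / 24.4 | 58.4 | 1.19 | 0.629 - 0.274 = 0.355 | same | 0.11-0.18 SD |

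Each bias range runs from 0.3 x the random-loss figure to 0.5 x the highest-propensity figure.

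**Check without the normal model.** Suppose instead that the measure is 1 SD worse in relapsers and that the arms differ in no other way. The true arm difference is 0.39 - 0.15 = 0.24 SD. Among completers it is (1 - f) x 0.39/(1 - 0.39f) - (1 - f) x 0.15/(1 - 0.15f), which gives 0.19 at f = 1/3, 0.16 at f = 1/2 and 0 at f = 1. The direction is the same.

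**Share of non-relapsers.** With no loss it is (34.0 + 24.4)/80 = 73%. Among completers it is 58.4/72.8 = 80% at f = 1/3 and 58.4/69.2 = 84% at f = 1/2.

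**The case against.** The strongest reply is that the document never says incomplete cases are deleted. This is correct: deletion is the usual behaviour of the method named, not plan text. But no alternative is given, and the remedy is to write one down.

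Several stronger readings are tempting and are not supported:

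- **A reader might take 58 of 80 as the expected loss.** That applies 3-month relapse rates to a scan which section 2.d places at 4 weeks. It is the relapse-only upper bound, relevant if the third time point is at 3 months, as section 4.c implies, and every relapser misses it.
- **A reader might conclude that the ANOVA turns the aim into a question about non-relapsers.** They are already 73% of the 80 with nothing missing. Over-representation is the accurate description.
- **A reader might treat drop-out as part of the primary outcome, or as differing by arm.** The relapse definition does not include it, and 15% vs 39% concerns relapse only.
- **A reader might infer that relapsers are withdrawn.** No section says so. Section 7.a mentions withdrawal in connection with adverse effects, and section 6.a refers to attempts to locate people who miss appointments.

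Two further objections reduce the point. The correlation of 0.3-0.5 is assumed, and section 2.d says no effect sizes are available for baseline fMRI signal by later lapse. A group-by-time test also uses change, so any part of relapse propensity already visible at baseline would partly cancel. Finally, section 6.a lists assessments at weeks 2, 4, 6, 8 and 12 separately from the three scans, so a missed scan need not remove craving ratings or drug-use data collected there.

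These objections narrow the scope and shrink the numbers. They do not supply a method for loss that the plan itself links to outcome.

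**Conclusion.** The concern holds in a limited form. The plan anticipates outcome-related loss at the third scan, assumes that this outcome differs by arm, and names an analysis that, as normally run, discards incomplete participants along with their earlier valid data. It is firmest for fMRI and in-scanner craving. It is weaker for other craving ratings and for days of drug use, although the latter is assigned the same ANOVA. The primary chi-square test of relapse is not affected.

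On the 4-week timing, a modest effect is the more plausible one: around 69 to 73 of 80 kept, a standard error 5-8% larger, and 0.02-0.09 SD of bias towards no difference. The upper bound in the working applies only on the 3-month reading with every relapser lost. All of this rests on 1:1 allocation, the plan's relapse rates, relapse as the sole cause of loss, and an assumed correlation. Treatment drop-out would add loss that the document does not quantify. The direction of bias also depends on the intervention reducing relapse as assumed.

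**What to change.** 1. In section 4.c, replace the UH3 2x3 ANOVA for fMRI, subjective measures and days of drug use with a likelihood-based repeated-measures mixed model. Include all randomised participants with any usable observation and report the arm difference at each post-baseline time point. Use a count-appropriate form for days of use if needed.
2. State that participants who relapse or stop maintenance treatment are still invited to the third scan and the remaining research assessments. This concerns data collection only.
3. Add one sensitivity analysis that shifts the missing third-scan values of relapsers and drop-outs towards a worse response.
4. Reconcile the timing of the third scan, which is 4 weeks in section 2.d, with the 3-month target in section 4.c.

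The cost is SAP wording and slightly more analysis. Section 6.a already lists three scans per UH3 participant, so no new visit type or extra participants are needed. The mixed model still assumes data are missing at random given what was observed, and item 3 tests that assumption.
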